### 11.3.7 Estimand strategy

The estimand strategy is specified in terms of the variable type, e.g. continuous, binary/categorical, and time-to-event. A primary analysis will be pre-specified for each

THIS DOCUMENT CONTAINS CONFIDENTIAL INFORMATION AND MUST NOT BE COPIED OR MADE AVAILABLE TO ANY THIRD PARTY  
WITHOUT THE PRIOR WRITTEN CONSENT OF THE LEO PHARMA GROUP

estimand and pre-specified sensitivity analyses will be conducted to assess the robustness of the results with respect to departures from the statistical assumptions of the primary analysis.

### Description of intercurrent events

An intercurrent event refers to a post-baseline event that affects either the interpretation or the existence of the measurements of an endpoint. For the purposes of this trial, we define the following 2 intercurrent events:

- ***Initiation of rescue treatment:*** This event occurs when a subject initiates rescue treatment as listed in no. 1-6 of Section 6.7 for intolerable AD signs and/or symptoms. The timing of the event will be taken as the date of initiation of the rescue treatment recorded in the eCRF.
- ***Permanent discontinuation of IMP:*** This event occurs when a subject permanently discontinues IMP. This event can occur either at the subject's own initiative or at the investigator's or sponsor's discretion. The timing of the event will be taken as the date of permanent discontinuation of IMP as recorded in the eCRF.

[Panel 16](#) provides an overview of the estimand strategies defined in Sections 11.3.7.1, 11.3.7.2, and 11.3.7.3 that will be used to address occurrences of the intercurrent events described above.

An overview of statistical analysis of endpoints can be found in [Panel 17](#).

THIS DOCUMENT CONTAINS CONFIDENTIAL INFORMATION AND MUST NOT BE COPIED OR MADE AVAILABLE TO ANY THIRD PARTY WITHOUT THE PRIOR WRITTEN CONSENT OF THE LEO PHARMA GROUP

**Panel 16: Handling of observed and missing data according to intercurrent events in the primary analysis of the estimands defined in Sections 11.3.7.1, 11.3.7.2, and 11.3.7.3**

Events	Observed data or missing	Continuous endpoints			Binary endpoints		TTE endpoints
		Primary Estimand	Hypothetical Suppl. Estimand	Second Suppl. Estimand	Primary Estimand	Suppl. Estimand	
Initiation of rescue treatment	Observed	Treated as missing, MI	Treated as missing, MI	Value will be used as observed	NRI	Value will be used as observed	Not applicable
	Missing	MI	MI	MI	NRI	MI	Not applicable
Permanent discontinuation of IMP, for reasons other than lack of efficacy or an AE related to worsening of AD	Observed	Treated as missing, MI	Treated as missing, MI	Value will be used as observed	Treated as missing, MI	Value will be used as observed	Accounted for as a competing risk a
	Missing	MI	MI	MI	MI	MI	Accounted for as a competing risk a
Permanent discontinuation of IMP, due to lack of efficacy or an AE related to worsening of AD	Observed	Treated as missing, LOCF	Treated as missing, MI	Value will be used as observed	NRI	Value will be used as observed	Accounted for as a competing risk a
	Missing	LOCF	MI	MI	NRI	MI	Accounted for as a competing risk a

THIS DOCUMENT CONTAINS CONFIDENTIAL INFORMATION AND MUST NOT BE COPIED OR MADE AVAILABLE TO ANY THIRD PARTY WITHOUT THE PRIOR WRITTEN CONSENT OF THE LEO PHARMA GROUP

Events	Observed data or missing	Continuous endpoints			Binary endpoints		TTE endpoints
		Primary Estimand	Hypothetical Suppl. Estimand	Second Suppl. Estimand	Primary Estimand	Suppl. Estimand	
No intercurrent events	Observed	Value will be used as observed	Value will be used as observed	Value will be used as observed	Value will be used as observed	Value will be used as observed	Not applicable
	Missing	MI	MI	MI	MI	MI	Not applicable

a) Withdrawal from trial will also be accounted for as a competing risk.

**Abbreviations:** AD = atopic dermatitis; AE = adverse event; IMP = investigational medicinal product; LOCF = last observation carried forward; MI = multiple imputation; NRI = non-responder imputation; Suppl. = supplementary; TTE = time-to-event.

THIS DOCUMENT CONTAINS CONFIDENTIAL INFORMATION AND MUST NOT BE COPIED OR MADE AVAILABLE TO ANY THIRD PARTY WITHOUT THE PRIOR WRITTEN CONSENT OF THE LEO PHARMA GROUP

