## 6.5 Rescue treatment

Rescue treatment is defined as the use of any of the prohibited medications or procedures listed in no. 1-6 of Section 6.7 initiated to treat intolerable AD signs and/or symptoms during the treatment and follow-up period. Rescue treatment for AD may be prescribed to trial subjects at the discretion of the investigator.

- In case rescue treatment is initiated before Week 4:
  - IMP will be permanently discontinued (see Section 7.2.1).
- In case rescue treatment is initiated at or after Week 4:
  - Subjects should preferably be started on topical treatment (TCS and/or TCI), and these subjects will continue IMP and the schedule of trial visits and assessments. Rescue treatment should only be used in situations where the subject is at risk of discontinuation, and should be continued for as short a period as possible.

*Note: It is recommended that the investigator starts with a TCI or least potent TCS for the face (e.g. hydrocortisone 1%, 2.5% cream/ointment) and moderately potent TCS for the body (e.g. triamcinolone acetonide 0.1% cream/ointment).*

- If the subject experiences intolerable AD signs and/or symptoms and the TCS and/or TCI rescue treatment is insufficient, the subject might need to progress to other rescue treatment or procedures listed in Section 6.7. In that case, IMP will be permanently discontinued (see Section 7.2.1).
- In case rescue treatment is initiated at or after Week 16:
  - If the subject experiences intolerable AD signs and/or symptoms during the follow-up period (Week 16 to 32), topical and systemic rescue treatment or procedures listed in Section 6.7 may be prescribed at the discretion of the investigator. In such case, subjects will continue the schedule of trial visits and assessments.

Investigators should make every attempt to conduct efficacy and safety assessments (for example disease severity scores, safety laboratory assessments) immediately before administering rescue treatment. An unscheduled visit may be used for this purpose, if necessary.

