## 6.7 Prohibited medications and procedures

The medications and procedures listed below are prohibited during the trial from randomization (Week 0). Medications and procedures disallowed prior to randomization are covered by the exclusion criteria (see Section 5.3). In case any prohibited treatments are used during the trial, they must be recorded in the eCRF as concomitant medication.

THIS DOCUMENT CONTAINS CONFIDENTIAL INFORMATION AND MUST NOT BE COPIED OR MADE AVAILABLE TO ANY THIRD PARTY WITHOUT THE PRIOR WRITTEN CONSENT OF THE LEO PHARMA GROUP

From randomization through the last follow-up visit (Week 32), the below treatments are prohibited:

1. TCS and TCI.
2. Topical PDE-4 inhibitors.
3. Topical JAK inhibitors.
4. Use of UVA or UVB, PUVA, other phototherapy, tanning beds, or prolonged sun exposure.
5. Systemic corticosteroids (nasal, ophthalmic, and inhaled corticosteroids are allowed).
6. Systemic treatment with immunosuppressive drugs (e.g. methotrexate, cyclosporine, azathioprine), immunomodulating drugs, JAK inhibitors, and retinoids (e.g. alitretinoin).
7. Biological products.
8. Investigational agents other than LEO 138559.
9. Allergen immunotherapy.
10. Live (attenuated) vaccine.
11. Immunoglobulins.
12. Blood products.

Prescription of prohibited medications and procedures in no. 1-6 do not constitute a protocol deviation if given as rescue treatment for AD (Section [6.5](#)). If prohibited medications and procedures are used for reasons other than rescue treatment for AD, they must be recorded as protocol deviations and IMP will be permanently discontinued (see Section [7.2.1](#)).

Please note that receipt of inactive/killed vaccines (e.g. inactive influenza) is allowed, provided that they are not administered within 5 days before/after any trial visit.

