### 7.2 Reasons for discontinuation of IMP

#### 7.2.1 Reasons for permanent discontinuation of IMP

Subjects will permanently discontinue IMP in the event of:

- Evidence of pregnancy, or if the subject is non-compliant with the contraception requirements (see inclusion criterion no. 10).
- An AE that, in the opinion of the investigator or sponsor's medical expert, contraindicates further dosing.
- Withdrawal by subject.
- Protocol-specified withdrawal criterion met, defined as initiation of:
  - Any rescue treatment before Week 4.
  - Prohibited medication (except use of rescue treatment with TCS and/or TCI at or after Week 4, see Section 6.5).
- Other reasons, at the discretion of the investigator. If other, a specification should be provided.

For requirements specific for EU countries i.e. CZ, DE, ES, FR, HU, PL and RO, see Section 12.5.1)

THIS DOCUMENT CONTAINS CONFIDENTIAL INFORMATION AND MUST NOT BE COPIED OR MADE AVAILABLE TO ANY THIRD PARTY WITHOUT THE PRIOR WRITTEN CONSENT OF THE LEO PHARMA GROUP

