## Data to be recorded in the eCRF

The date and time of last dose for IMP will be recorded in the eCRF. The primary reason for permanent discontinuation of IMP must be recorded in the medical records and on the end-of-treatment form in the eCRF, e.g.:

- Death.
- Pregnancy.
- AE (if AE, a specification must be provided).
- Lost to follow-up.
- Lack of efficacy.
- Randomized by mistake.
- Withdrawal by subject.
- Protocol-specified withdrawal criterion met.
- Other (if other, a specification should be provided).

In case the primary reason is AE, the AE in question will be linked to the permanent discontinuation of IMP.

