#### **11.3.8.2 Analysis of primary estimand for binary endpoints**

Subjects receiving rescue treatment or who have permanently discontinued IMP due to lack of efficacy, or the occurrence of an AE related to worsening of AD, prior to the endpoint of interest, are defined as non-responders, reflecting an assumption that the occurrence of such intercurrent events indicates a failure of the randomized treatment.

Data observed after the permanent discontinuation of IMP for reasons besides lack of efficacy or the occurrence of an AE related to worsening of AD will be excluded from the analysis and treated as missing. Missing data and data treated as missing will be imputed using MI (100 iterations) under a MAR assumption within each treatment group. All subject-level data observed prior to the occurrence of an intercurrent event will be used to inform the imputation

THIS DOCUMENT CONTAINS CONFIDENTIAL INFORMATION AND MUST NOT BE COPIED OR MADE AVAILABLE TO ANY THIRD PARTY WITHOUT THE PRIOR WRITTEN CONSENT OF THE LEO PHARMA GROUP

models. Further details regarding the specification of the imputation models will be specified in the SAP.

The 100 complete datasets will be analyzed based on a logistic regression model, including treatment, baseline disease severity (vIGA-AD score at baseline), region (Japan, Other countries), prior use of biologics or systemic JAK inhibitors for AD (Yes/No) and the baseline value of the endpoint as a covariate. The logistic regression model will be used to estimate the risk, risk difference, and associated 95% CI based on the standardized estimator presented in Bartlett (80). For the analysis of the vIGA-AD responder endpoints, baseline disease severity will not be included as a covariate in the logistic regression model.

The pooled estimate of the risk difference, along with the associated 95% CIs and nominal p-values will be presented. Inference will be based on applying Rubin's rules to the estimates obtained from the analysis of the imputed data sets using the standardized estimator.

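### A biologic started for AD falls outside the rescue definition, so a subject with no earlier rescue may be imputed where a JAK inhibitor or cyclosporine would mean non-response

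*Combined protocol and SAP*

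**What the plan says.** Section 6.5 sets the scope of rescue: "Rescue treatment is defined as the use of any of the prohibited medications or procedures listed in no. 1-6 of Section 6.7". Section 11.3.7 repeats the same range for the intercurrent event: "This event occurs when a subject initiates rescue treatment as listed in no. 1-6 of Section 6.7 for intolerable AD signs and/or symptoms". In Section 6.7, item 6 holds systemic immunosuppressants, immunomodulating drugs, JAK inhibitors and retinoids; item 7 is biological products.

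Section 6.7 exempts only items 1-6 from being a deviation: "Prescription of prohibited medications and procedures in no. 1-6 do not constitute a protocol deviation if given as rescue treatment for AD". For prohibited treatment used otherwise, "they must be recorded as protocol deviations and IMP will be permanently discontinued". Section 7.2.1 agrees, naming as a reason to stop IMP: "Prohibited medication (except use of rescue treatment with TCS and/or TCI at or after Week 4, see Section 6.5". The eCRF takes one primary reason for the stop. One option is "Protocol-specified withdrawal criterion met", listed apart from lack of efficacy and from AE.

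For the primary binary estimand, Section 11.3.8.2 makes a subject a non-responder after rescue, or after an IMP stop for lack of efficacy or an AD-worsening AE. Its other branch begins "Data observed after the permanent discontinuation of IMP for reasons besides lack of efficacy" (or an AD-worsening AE) and sends those data to MI under MAR within the arm. The matching row of Panel 16 is "Permanent discontinuation of IMP, for reasons other than lack of efficacy or an AE related to worsening of AD".

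**The concern.** Two subjects with the same flare and the same lack of benefit can be classified differently because of the drug class chosen. The plan gives no reason for the distinction. Its rationale in Section 11.3.8.1, that a subject needing rescue would not have got better by staying on IMP, fits a switch to a biologic at least as well as a switch to cyclosporine.

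For the biologic, failure status then rests on which stop reason the site selects, and a specific non-failure option is available. The outcomes at stake are the primary binary estimand (EASI-50 to EASI-100, vIGA-AD 0/1, ADSD response) and the baseline subgroup estimands that copy its rules.

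**Working it through.** **Tracing the text.** Take a subject with no earlier item 1-6 rescue who starts systemic treatment for AD before the Week 16 assessment.

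| Step | JAK inhibitor or cyclosporine (item 6) | Biologic (item 7) |
|---|---|---|
| Rescue under 6.5 and 11.3.7? | Yes | No |
| IMP stopped (6.7, 7.2.1)? | Yes | Yes |
| Primary binary estimand | Non-responder, any stop code | MI, unless coded lack of efficacy or AD-worsening AE |
| Percent change in EASI, 11.3.8.1 text | LOCF | MI, same exception |
| Percent change in EASI, Panel 16 | MI | MI, or LOCF if so coded |
| Time to rescue, primary | Event | Competing risk, through the IMP stop |
| Time to rescue, composite supplementary | Event | Event, through the IMP stop |

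The treatment-policy estimands use observed values for both. A subject who stops IMP as withdrawal by subject, stays for visits as Section 7.4 asks, and then starts one of these drugs differs in the same way on the binary endpoints.

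**Size per subject.** The plan states no figure to reproduce. Moving one subject from non-response to MI with response probability p changes the rate in an arm of 50 by p/50. For p from 0.05 to 0.5 that is 0.1 to 1.0 points.

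**A plausible p.** The imputation model is left to the SAP, so the sample size model in Section 11.1 stands in: Panel 14 means, variance 111.0, covariance 32.5. Assumed: baseline EASI 28 (range 20 to 36), no change at Weeks 1, 2, 3, 4, 6 and 8, then the stop. The model's baseline-EASI effect is not given and is left out.

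- Weight per observed visit: 32.5 / (111 + 5 × 32.5) = 0.1188.
- Conditional SD at Week 16: √(111 − 6 × 32.5² / 273.5) = 9.37.
- Conditional mean change, regimen 1: −20.7 + 0.1188 × 86.6 = −10.4. Regimen 4: −10.0 + 0.1188 × 41.6 = −5.1. Placebo: −3.5 + 0.1188 × 23.7 = −0.7. (86.6, 41.6 and 23.7 are the sums of the assumed reductions at the six visits.)
- EASI-50 at baseline 28 needs a change of −14 or lower. Regimen 1: Φ((−14 + 10.4)/9.37) = 35%. Regimen 4: 17%. Placebo: 8%. Over baselines 36 to 20 the ranges are 21-52%, 8-30% and 3-16%. Non-responder imputation gives 0%.

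One such subject in regimen 1 adds 0.35/50 = 0.7 points to its EASI-50 rate; one in placebo adds 0.08/50 = 0.16 points.

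**Effect on regimen 1 minus placebo (EASI-50), by assumed counts.**

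- 3 and 3: (3 × 35 − 3 × 8)/50 = +1.6 points.
- 1 and 3: (35 − 24)/50 = +0.2 points.
- 0 and 3: −24/50 = −0.5 points.

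**Primary endpoint, 11.3.8.1 text only.** MI credits a mean improvement of about 10.4/28 = 37% in regimen 1 and 0.7/28 = 2.5% in placebo, against 0% under LOCF. With 3 and 3 the difference grows by 3 × (37 − 2.5)/50 = 2.1 points. The planning difference at the same baseline is (20.7 − 3.5)/28 = 61%. Under Panel 16 the effect is nil, because rescue also gets MI.

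**The case against.** The best counter-argument is that few subjects can reach the gap. From Week 4, Section 6.5 prefers TCS or TCI first, and a subject who has used either is already a non-responder before any biologic. This stands and narrows the point to direct starters. It does not close the gap, because the order is a preference.

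Sites may also code the stop as lack of efficacy or as an AE. Section 12.2.4 requires AD worsening beyond normal fluctuation to be reported as an AE, and Section 11.3.7.2 leaves the list of AD-worsening AEs to the SAP. Some cases will be caught this way, but nothing requires it.

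Two looser readings would bring biologics inside rescue: immunomodulating drugs in item 6, and the escalation sentence in Section 6.5 that cites Section 6.7 without a range. The first leaves item 7 with little purpose and sits badly with exclusion criteria 20 and 23, which separate the two groups. The second speaks of other rescue treatment, which the same section has already limited to items 1-6.

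The binary tipping-point analysis would bound the effect if its range, left to the SAP, includes zero response among imputed active subjects. It cannot separate biologic starters from other imputed subjects.

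A reader might take the seven placebo subjects in phase 2a who stopped as withdrawal by subject (Section 2.2.2) as a sign of frequency. They are not: nothing there mentions biologics. Section 2.1 on the place of biologics likewise describes routine care, not conduct in a 16-week blinded trial.

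Finally, counting a biologic started after an unrelated IMP stop as failure may look harsh. The existing rule for items 1-6 already does this, so the change gives only parity.

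**Conclusion.** The gap is real on the text but narrow. It covers a biologic started for AD before the Week 16 assessment, without earlier item 1-6 rescue, where the IMP stop is not coded as lack of efficacy or an AD-worsening AE. The documents do not say how many subjects this will be; probably few. At about 0.7 points per subject in regimen 1 (p = 0.35, resting on the assumed baseline, the assumed lack of improvement and the stand-in model), the effect on any one response rate is small.

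Two stronger conclusions are tempting and not supported. One is that the gap favours LEO 138559: the credit per subject is larger in regimen 1 than in placebo, but more starters in placebo could cancel or reverse it. The other is that the primary endpoint is compromised: its estimand has no failure category, and the difference exists only if the LOCF text of Section 11.3.8.1 is followed rather than Panel 16. The affected binary endpoints are exploratory and outside the testing hierarchy. This is a cheap improvement to consistency.

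**What to change.** For the estimands only (Section 11.3.7, Panel 16, Sections 11.3.8.1 and 11.3.8.2), define rescue as any treatment in Section 6.7 items 1-7 initiated for intolerable AD before the Week 16 assessment, dated by its start date and handled exactly as item 1-6 rescue is. Derive it from the indication and start date that Section 6.6 already collects, and settle the rule before unblinding. A biologic remains a protocol deviation that stops IMP; only its classification in the analysis changes.

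The cost is one extra derived flag and possibly slightly lower response rates. No new data are needed.

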## Panel 17: Statistical analysis of endpoints

Endpoint	Estimands to be analyzed
Percent change in EASI score from baseline to Week 16.	Primary estimand for continuous endpoints. Hypothetical supplementary estimand for continuous endpoints. Second supplementary estimand for continuous endpoints.
Achievement of EASI-50 at Week 16.	Primary estimand for binary endpoints. Supplementary estimand for binary endpoints.
Achievement of EASI-75 at Week 16.	Primary estimand for binary endpoints. Supplementary estimand for binary endpoints.
Achievement of EASI-90 at Week 16.	Primary estimand for binary endpoints. Supplementary estimand for binary endpoints.
Achievement of EASI-100 at Week 16.	Primary estimand for binary endpoints. Supplementary estimand for binary endpoints.
Change in EASI score from baseline to Week 16.	Primary estimand for continuous endpoints. Hypothetical supplementary estimand for continuous endpoints.
Change in SCORAD score from baseline to Week 16.	Primary estimand for continuous endpoints. Hypothetical supplementary estimand for continuous endpoints.
Percent change in SCORAD score from baseline to Week 16.	Primary estimand for continuous endpoints. Hypothetical supplementary estimand for continuous endpoints.
Achievement of vIGA-AD score of 0 (clear) or 1 (almost clear) at Week 16.	Primary estimand for binary endpoints. Supplementary estimand for binary endpoints.
Change in BSA from baseline to Week 16.	Primary estimand for continuous endpoints. Hypothetical supplementary estimand for continuous endpoints.
Percent change in BSA from baseline to Week 16.	Primary estimand for continuous endpoints. Hypothetical supplementary estimand for continuous endpoints.
Reduction of ADSD Worst █ score (weekly average) $\geq 4$ from baseline to Week 16.	Primary estimand for binary endpoints. Supplementary estimand for binary endpoints.
Change in DLQI (and individual domain scores) from baseline to Week 16.	Primary estimand for continuous endpoints. Hypothetical supplementary estimand for continuous endpoints.
Percent change in DLQI (and individual domain scores) from baseline to Week 16.	Primary estimand for continuous endpoints. Hypothetical supplementary estimand for continuous endpoints.
Change in POEM score (and individual item scores related to itch and sleep) from baseline to Week 16.	Primary estimand for continuous endpoints. Hypothetical supplementary estimand for continuous endpoints.

THIS DOCUMENT CONTAINS CONFIDENTIAL INFORMATION AND MUST NOT BE COPIED OR MADE AVAILABLE TO ANY THIRD PARTY  
WITHOUT THE PRIOR WRITTEN CONSENT OF THE LEO PHARMA GROUP

Endpoint	Estimands to be analyzed
Percent change in POEM score from baseline to Week 16.	Primary estimand for continuous endpoints. Hypothetical supplementary estimand for continuous endpoints.
Change in EQ-5D-5L index score from baseline to Week 16.	Primary estimand for continuous endpoints. Hypothetical supplementary estimand for continuous endpoints.
Percent change in EQ-5D-5L index score from baseline to Week 16.	Primary estimand for continuous endpoints. Hypothetical supplementary estimand for continuous endpoints.
Change in EQ-5D-5L VAS score from baseline to Week 16.	Primary estimand for continuous endpoints. Hypothetical supplementary estimand for continuous endpoints.
Percent change in EQ-5D-5L VAS score from baseline to Week 16.	Primary estimand for continuous endpoints. Hypothetical supplementary estimand for continuous endpoints.
Change in HADS score from baseline to Week 16.	Primary estimand for continuous endpoints. Hypothetical supplementary estimand for continuous endpoints.
Percent change in HADS score from baseline to Week 16.	Primary estimand for continuous endpoints. Hypothetical supplementary estimand for continuous endpoints.
Change in Difficulty [REDACTED] (weekly average) from baseline to Week 16.	Primary estimand for continuous endpoints. Hypothetical supplementary estimand for continuous endpoints.
Percent change in Difficulty [REDACTED] (weekly average) from baseline to Week 16.	Primary estimand for continuous endpoints. Hypothetical supplementary estimand for continuous endpoints.
Change in Nocturnal [REDACTED] (weekly average) from baseline to Week 16.	Primary estimand for continuous endpoints. Hypothetical supplementary estimand for continuous endpoints.
Percent change in Nocturnal [REDACTED] (weekly average) from baseline to Week 16.	Primary estimand for continuous endpoints. Hypothetical supplementary estimand for continuous endpoints.
Change in Frequency of [REDACTED] During the Night (weekly average) from baseline to Week 16.	Primary estimand for continuous endpoints. Hypothetical supplementary estimand for continuous endpoints.
Percent change in Frequency of [REDACTED] During the Night (weekly average) from baseline to Week 16.	Primary estimand for continuous endpoints. Hypothetical supplementary estimand for continuous endpoints.
Change in WPAI-SHP domain scores from baseline to Week 16.	Primary estimand for continuous endpoints. Hypothetical supplementary estimand for continuous endpoints.

THIS DOCUMENT CONTAINS CONFIDENTIAL INFORMATION AND MUST NOT BE COPIED OR MADE AVAILABLE TO ANY THIRD PARTY WITHOUT THE PRIOR WRITTEN CONSENT OF THE LEO PHARMA GROUP

Endpoint	Estimands to be analyzed
Percent change in WPAI-SHP domain scores from baseline to Week 16.	Primary estimand for continuous endpoints. Hypothetical supplementary estimand for continuous endpoints.
Change in SCORAD Part C (Pruritus VAS) score from baseline to Week 16.	Primary estimand for continuous endpoints. Hypothetical supplementary estimand for continuous endpoints.
Percent change in SCORAD Part C (Pruritus VAS) score from baseline to Week 16.	Primary estimand for continuous endpoints. Hypothetical supplementary estimand for continuous endpoints.
Time from baseline to use of any rescue treatment.	Primary estimand for time-to-event endpoints. Supplementary estimand for time-to-event endpoints
Reduction of ADSD Worst [REDACTED] score (weekly average) $\geq 4$ from baseline to Week 16.	Baseline subgroup estimand.
Reduction of DLQI $\geq 4$ from baseline to Week 16.	Baseline subgroup estimand.
Reduction of POEM $\geq 4$ from baseline to Week 16.	Baseline subgroup estimand.

**Abbreviations:** ADSD = Atopic Dermatitis Symptom Diary; BSA = body surface area; DLQI = Dermatology Life Quality Index; EASI = Eczema Area and Severity Index; EASI-50 = at least 50% reduction in EASI score; EASI-75 = at least 75% reduction in EASI score; EASI-90 = at least 90% reduction in EASI score; EASI-100 = 100% reduction in EASI score; EQ-5D-5L = EuroQoL 5 Dimension Health Questionnaire 5 Level; HADS = Hospital Anxiety and Depression Scale; POEM = Patient-Oriented Eczema Measure; SCORAD = SCORing Atopic Dermatitis; VAS = Visual Analogue Scale; vIGA-AD = validated Investigator Global Assessment Scale for Atopic Dermatitis; WPAI-SHP = Work Productivity and Activity Impairment: Specific Health Problem.

